3.2.3 Safety

All safety data will be included in the data listings and summary tables will be based on the safety population.

3.2.3.1 Adverse events

AEs reported in the case report form (CRF) will be coded using the medical dictionary for regulatory activities (MedDRA) Version 19.0 or higher.

All adverse events and SAEs, including pre-treatment events which occurred during the screening period will be reported from the time of consent until the EOS visit.

Listings will be presented and sorted by subject, start date-time of AEs, primary system organ class, preferred term and verbatim text for all adverse events recorded during the study.

Listings of all AEs, serious adverse events (SAE), adverse events leading to withdrawal and listing of deaths will also be presented.

Treatment Emergent Adverse Events (TEAE) will be flagged (*) in the adverse events listing and will be summarised.

A TEAE is defined as any AE that occurs during the active phase of the study if:

- it was not present prior to receiving dose of Smecta®, or
- it was present prior to receiving the dose of Smecta® but the intensity increased during the active phase of the study, or
- it was present prior to receiving the dose of Smecta®, the intensity is the same but the drug relationship became related during the active phase of the study.

An overall summary table of all AEs will be presented.

TEAEs will be summarised with the number and percentage of subjects with adverse events classified by primary system organ class (SOC) and preferred term (PT). The number of occurrences of a TEAE will also be presented.

In addition, the same summary tables will also be presented for SAEs, TEAEs per decreasing frequency, TEAEs by maximum intensity, TEAEs by most serious causality and TEAEs leading to withdrawal.

In the event of multiple adverse events being reported by the same subject, the maximum intensity (severe > missing > moderate > mild) and the most serious causality (related > not related) will be chosen.

3.2.3.2 Laboratory data

A separate listing of normal ranges for international system (SI) units will be provided by gender and age where relevant.

Laboratory data (haematology, biochemistry, coagulation and urinalysis) will be listed in SI units and abnormal values will be flagged (High, [H], Low [L], clinically significant [CS]) where applicable. Any unscheduled laboratory assessments will be flagged [U] in the listings.

In addition, a listing will be presented of all values for a subject with at least one clinically significant abnormal laboratory value.

The baseline will be defined as the last available (and reliable if applicable) assessment collected prior to receiving dose of Smecta® on Day 1.

For haematology, biochemistry and coagulation, summary statistics will be presented at each scheduled assessment and absolute changes from baseline. For haematology and biochemistry, shift tables from baseline to post baseline visit (EOS visit) will be presented using the number and percentage of subjects with low, normal or high values.

For continuous urinalysis, summary statistics will be presented at each scheduled assessment for actual values and absolute changes from baseline.

Categorical urinalysis parameters (absent/trace/positive) will be presented in frequency tables at each scheduled assessment as well as subjects with low, normal or high urinary values.

3.2.3.3 Physical examination

Physical examination will be listed by subject, timepoint and examination date.

3.2.3.4 Vital signs

Vital signs (supine systolic and diastolic blood pressure (SBP & DBP), heart rate (HR), body weight, and aural body temperature) will be listed at each assessment by subject (and so including clinically significant findings). Any unscheduled vital signs will be flagged [U] in the listing.

The baseline will be defined as the last available (and reliable if applicable) assessment collected prior to receiving dose of Smecta® on Day 1.

Summary statistics will be presented at each scheduled assessment for actual values and absolute changes from baseline.

Shift tables for heart rate and blood pressure (systolic and diastolic) will be presented with the number and percentages of subjects with values of potential clinical importance (VPCI):

-Systolic blood pressure (mmHg) will have three categories:

<120	Low
[120-129]	Normal
>129	High

-Diastolic blood pressure (mmHg) will have three categories:

<80	Low
[80-84]	Normal
>84	High

-Heart rate (bpm) will have three categories:

<60	Low
[60-100]	Normal
>100	High

The VPCI will be flagged in the listings and the flagging identifier specified.

The temperature will be listed by subject, timepoint and examination date.

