4.3 Inclusion Criteria

Potential study subjects may be entered in the study if they meet all of the following criteria:

- (1) Provision of written informed consent prior to any study related procedure.
- (2) Male or female subjects aged between 18 and 60 years (inclusive) at the time of giving informed consent.
- (3) Subjects with chronic functional diarrhoea defined as "Loose (mushy) or watery stools according to Bristol scale grade 6 and 7, occurring in at least 75% of stools for the last 3 months with symptoms onset at least 6 months before diagnosis, without or with pain (including Irritable Bowel Syndrome)" as documented in subject's medical history.
- (4) Body Mass Index (BMI) between 19 and 32 kg/m² (inclusive), with minimum body weight of 50 kg, at screening.

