1.2.1 Study population

A total of 35 subjects will be enrolled in order to ensure at least 29 subjects completing the study. It is planned to enrol a minimum of 40% of each gender, with gender distributed approximately equally between sites (e.g. no site with less than 35% of one gender).

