1.3.2.3 Safety assessments

The safety assessments are:

- Adverse events (AEs) monitored from the time that the subject gives informed consent and throughout the study
- Clinical safety assessments:

- Physical examination at screening and EOS visit;
- Vital signs measured at screening and EOS visit, including supine systolic and diastolic blood pressure (SBP & DBP), heart rate (HR), body weight, and aural body temperature;
- 12-lead electrocardiograms (ECGs) measured at screening and EOS visit, including interpretation with clinical significance, sinus rhythm, respiratory rate (RR) interval duration or heart rate (HR), PR interval duration, QRS interval duration, time interval for ventricular depolarisation and repolarisation (QT) interval duration, corrected QT interval (QTc) interval corrected by the Bazett correction method;
- Clinical laboratory tests, including clinical significance, measured at screening, D-1 and EOS visit:
 - Haematology: full blood count including red blood cells (RBC) count, haemoglobin, haematocrit, mean corpuscular volume (MCV), mean cell haemoglobin (MCH), mean cell haemoglobin concentration (MCHC), white blood cell (WBC) count with differential count (neutrophils, eosinophils, basophils, lymphocytes, monocytes), platelet count;
 - Blood biochemistry: urea, creatinine, total bilirubin, conjugated bilirubin, chloride, bicarbonate, sodium, potassium, calcium, inorganic phosphate, alkaline phosphatase (ALP), aspartate aminotransferase (AST), alanine aminotransferase (ALT), gamma-glutamyl transpeptidase (GGT), amylase, lipase, albumin, total protein, total cholesterol, triglycerides, fasting glucose, iron, transferrin saturation, ferritin, eGFR, haemoglobin A1c (HbA1c), urate, C reactive protein (only at screening);
 - Coagulation: activated partial thromboplastin time (APTT), prothrombin time, prothrombin ratio, international normalised ratio (INR);
 - Urinalysis: pH, proteins, ketones, glucose, bilirubin, urobilinogen, occult blood, Nitrite, Microscopic examination of sediment (if indicated)
 - Pregnancy tests at screening, D-1 and EOS visit

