3.2.3.5 ECG

Interpretation with clinical significance, sinus rhythm, respiratory rate (RR) interval duration or heart rate (HR), PR interval duration, QRS interval duration, time interval for ventricular depolarisation and repolarisation (QT) interval duration, corrected QT interval (QTc) corrected by the Bazett correction method will be presented.

ECG results will be listed at each assessment by subject (and so including clinically significant findings).

Any unscheduled ECGs will be flagged [U] in the listing.

The baseline will be defined as the last available (and reliable if applicable) assessment collected prior to receiving dose of Smecta® on Day 1.

For continuous ECG parameters (RR, PR, QRS, QT and QTcB), summary statistics will be presented at each scheduled assessment for actual values and absolute changes from baseline.

Shift tables for heart rate, PR interval duration, QRS interval duration, QT interval duration and corrected QT interval will be presented with the number and percentages of subjects with values of potential clinical importance (VPCI):

-Heart rate (bpm) will have three categories:

<60	Low
[60-100]	Normal
>100	High

- PR interval duration (s) will have three categories:

<0.12	Low
[0.12-0.20]	Normal
>0.20	High

- QRS interval duration (s) will have two categories:

≤0.12	Normal
>0.12	High

- QT interval duration (s) will have two categories by each gender stratum:

Gender stratum	Normal	High
Males	<0.40	≥0.40
Females	<0.44	≥0.44

- Corrected QT interval (ms) will have two categories by each gender stratum:

Gender stratum	Normal	High
Males	≤440	>440
Females	≤460	>460

The VPCI will be flagged in the listings and the flagging identifier specified.

For interpretation of clinical significance (within normal limits / abnormal, not clinically significant / abnormal, clinically significant / not evaluable), a frequency table will be presented, by visit.

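### The SAP's blood-pressure bands are too narrow to serve as values of potential clinical importance, it does not say which categories count, and its uncorrected-QT limit disagrees with its own QTcB limit at lower heart rates

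*SAP*

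**What the plan says.** SAP 3.2.3.4 (Vital signs) plans shift tables for heart rate and blood pressure "with the number and percentages of subjects with values of potential clinical importance (VPCI"). Three categories are then given for each measure:

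- Systolic: Low below 120, Normal 120-129, High above 129 mmHg.
- Diastolic: Low below 80, Normal 80-84, High above 84 mmHg.
- Heart rate: Normal from 60 to 100 bpm.

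The section adds: "The VPCI will be flagged in the listings and the flagging identifier specified". It does not say whether Low, High or both are VPCI.

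SAP 3.2.3.5 (ECG) uses the same VPCI wording. There, "QT interval duration (s) will have two categories by each gender stratum": High from 0.40 s in men and from 0.44 s in women. Also, "Corrected QT interval (ms) will have two categories by each gender stratum": High above 440 ms in men and above 460 ms in women. The correction is Bazett's: "corrected QT interval (QTc) corrected by the Bazett correction method will be presented".

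The schedule gives one planned comparison per subject. SAP 1.3.2.3 has "Vital signs measured at screening and EOS visit", and the ECG has the same two time points.

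**The concern.** A reading of 118/78 is Low on both blood-pressure measures and, on one reading of the SAP, is flagged twice as potentially clinically important. The Normal bands cover ten and five whole mmHg values. That is narrow against plausible spread between subjects and between visits, and against the 40-bpm Normal band for heart rate in the same section.

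Two things are at stake. A flag that most subjects carry does not separate those who need attention. And with one arm and no control, a shift table in which many subjects move by chance cannot show whether the drug moved anyone.

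For QT, two rules under the same VPCI heading can give the same tracing opposite labels.

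**Working it through.** The documents state no expected flag rate and no distribution of blood pressure, heart rate or QT, so there is no plan figure to reproduce. All means, SDs and correlations below are assumptions for adults (Protocol 4.3: "Male or female subjects aged between 18 and 60 years (inclusive")). Category limits are from SAP 3.2.3.4 and 3.2.3.5. The number of subjects is from SAP 1.2.1: "A total of 35 subjects will be enrolled in order to ensure at least 29 subjects completing the study".

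**1. Ceiling on the Normal share, whatever the mean.** The largest share a band of half-width h can hold is 2Φ(h/SD) − 1.

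- Systolic, h = 5: 47% at SD 8, 32% at SD 12, 26% at SD 15. At least 53-74% fall outside.
- Diastolic, h = 2.5: 32% at SD 6, 25% at SD 8, 20% at SD 10. At least 68-80% fall outside.

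**2. One worked case.** Mean 120/76, between-subject SD 10/7, within-subject SD 8/6, readings rounded to whole mmHg.

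- Total SDs: √(10² + 8²) = 12.8 and √(7² + 6²) = 9.2.
- Systolic Normal: Φ((129.5 − 120)/12.8) − Φ((119.5 − 120)/12.8) = 29%.
- Diastolic Normal: Φ((84.5 − 76)/9.2) − Φ((79.5 − 76)/9.2) = 17%.
- Jointly, by simulation with systolic-diastolic correlation 0.6: about 93% are outside Normal on at least one measure (0.93 × 35 ≈ 33 of 35 subjects), and 31% are High on at least one.

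**3. Range of flag rates.** By simulation; correlation 0.5-0.7, except 0.6 in the 120/76 row.

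| Mean | SD | Low and High both count | Only High counts |
|---|---|---|---|
| 115/70 | 12/8 | 97% | 13% |
| 120/75 | 12/8 | 93-94% | 25-27% |
| 120/76 | 12.8/9.2 | about 93% | 31% |
| 125/80 | 12/8 | 90-91% | 44-47% |
| 124.5/82 | 8/6 | 80-83% | 42-45% |

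The last row centres both means in their bands with small SDs, so it favours the SAP.

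**4. Category changes with no drug effect.** Two visits per subject, by simulation.

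- The case in step 2: 44% change systolic category and 37% diastolic.
- Same SDs, systolic mean 115 to 125: 36-46%.
- Same SDs, diastolic mean 80: 44%; mean 72: 26%; mean 70: 20%.
- Mean 120/75, SD 12/8, visit-to-visit correlation 0.5 to 0.8: systolic 48% down to 33%, diastolic 34% down to 24%.

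Overall that is about 33-48% systolic and 20-44% diastolic. It does not depend on which categories are called VPCI, because the tables use all three.

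**5. Effect of merging Low with Normal.** In the step 2 case, chance changes fall from 44% to 22% (systolic) and from 37% to 19% (diastolic).

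**6. QT against QTcB.** QTcB = QT × √(HR/60). The two limits meet at HR = 60 × (QTc limit / QT limit)².

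- Men: 60 × (440/400)² = 72.6 bpm.
- Women: 60 × (460/440)² = 65.6 bpm.

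Below those rates a QT at its High limit has a Normal QTcB. At 60 bpm a man's 0.41 s is High on QT, yet its QTcB of 410 ms is Normal. At 55 bpm a woman's 0.44 s is High, yet QTcB is 440 × √(55/60) = 421 ms, which is Normal.

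Simulated flag rates on uncorrected QT, assuming heart-rate SD 10, QTcB mean 400-410 ms (men) or 415-425 ms (women) and QTcB SD 20:

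| Mean heart rate | Men | Women |
|---|---|---|
| 60 bpm | 50-61% | 28-36% |
| 65 bpm | 34-44% | 15-22% |
| 75 bpm | 10-16% | 3-5% |

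At a mean of 65 bpm, 87-95% of those flagged on QT have a Normal QTcB.

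**The case against.** The case for leaving this alone has four parts.

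- **The high flag rate rests on a reading the SAP does not state.** The section leaves the flagging identifier to be specified. If only High counts, the flagged share is a minority. This stands, so the 93% must always carry its condition. But the gap itself needs closing, and the chance shifts arise under either reading.
- **The distributions are assumed.** This stands too. Diastolic chance shifts fall to 20% at a mean of 70. The ceilings in step 1 need only an SD, and the QT crossover needs no assumed distribution.
- **QT and QTcB are different parameters.** Uncorrected QT varies with heart rate, so different labels are not in themselves an error. That is fair, but the SAP calls both potentially clinically important without saying which governs when they disagree.
- **Little depends on these tables.** SAP 3.1.6 rules out formal testing. Vital signs and ECG parameters also get continuous summaries with changes from baseline and full listings, and ECGs get a by-visit table of clinical interpretation. Protocol 7.1.4 sends clinically significant ECG abnormalities to adverse-event reporting. The only planned post-baseline value is at Day 125, 125 − 35 = 90 days after the last planned dose, so the tables would say little about on-treatment effects with any bands. All of this stands and limits the weight of the point.

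A reader might go further and infer that the QT limit also flags almost everyone, or that the safety output as a whole is uninterpretable. The documents support neither. The QT limit is one-sided and flags a minority in most scenarios, and the QTcB table and the other outputs just listed remain usable.

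**Conclusion.** The point holds as a minor one about reporting definitions.

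For blood pressure, the SAP should not present bands this narrow under a VPCI heading without saying which categories count. The flag rates of 80-97% (Low and High) and 13-47% (High only), and the chance shifts of 33-48% systolic and 20-44% diastolic, rest on assumed means, SDs and correlations. The direction is robust, because no mean brings most subjects inside either band at the SDs considered.

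For QT, the point is only that two rules in the same SAP disagree below 72.6 bpm in men and 65.6 bpm in women. That is arithmetic from the SAP's limits and Bazett's formula. How often it happens depends on the heart rates seen. The primary blood lead analysis is untouched.

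**What to change.** In SAP 3.2.3.4 and 3.2.3.5:

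1. State which categories are VPCI.
2. Do not flag the present blood-pressure bands as VPCI. Flag only values outside limits that the sponsor's medical lead sets in advance, or values that the investigator marks clinically significant. The second group overlaps with what the listings already show.
3. In the blood-pressure shift tables, merge Low with Normal unless the medical lead sets a separate lower limit. This roughly halves the chance shifts but does not remove them, so a footnote should say that movement between categories is expected without any drug effect.
4. Drop the uncorrected-QT shift table and rely on QTcB, or reconcile the two limits.

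The cost is a few table definitions and the matching listing flags. No data collection, sample size or primary analysis changes.

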3.2.3.5 ECG

Interpretation with clinical significance, sinus rhythm, respiratory rate (RR) interval duration or heart rate (HR), PR interval duration, QRS interval duration, time interval for ventricular depolarisation and repolarisation (QT) interval duration, corrected QT interval (QTc) corrected by the Bazett correction method will be presented.

ECG results will be listed at each assessment by subject (and so including clinically significant findings).

Any unscheduled ECGs will be flagged [U] in the listing.

The baseline will be defined as the last available (and reliable if applicable) assessment collected prior to receiving dose of Smecta® on Day 1.

For continuous ECG parameters (RR, PR, QRS, QT and QTcB), summary statistics will be presented at each scheduled assessment for actual values and absolute changes from baseline.

Shift tables for heart rate, PR interval duration, QRS interval duration, QT interval duration and corrected QT interval will be presented with the number and percentages of subjects with values of potential clinical importance (VPCI):

-Heart rate (bpm) will have three categories:

<60	Low
[60-100]	Normal
>100	High

- PR interval duration (s) will have three categories:

<0.12	Low
[0.12-0.20]	Normal
>0.20	High

- QRS interval duration (s) will have two categories:

≤0.12	Normal
>0.12	High

- QT interval duration (s) will have two categories by each gender stratum:

Gender stratum	Normal	High
Males	<0.40	≥0.40
Females	<0.44	≥0.44

- Corrected QT interval (ms) will have two categories by each gender stratum:

Gender stratum	Normal	High
Males	≤440	>440
Females	≤460	>460

The VPCI will be flagged in the listings and the flagging identifier specified.

For interpretation of clinical significance (within normal limits / abnormal, not clinically significant / abnormal, clinically significant / not evaluable), a frequency table will be presented, by visit.

3.2.3.6 Pregnancy tests

A listing with the date of examination, the status of the examination (done/not done/not applicable) and the result (positive/negative) will be provided by subject, timepoint, examination date and method: (serum on screening only or urine).

3.2.4 *Missing data and outliers*

3.2.4.1 *Missing data*

No missing value will be imputed.

If a value required a retest, the last reliable non-missing value will be taken into account if measured before the administration of Smecta®; and the first non-missing reliable value for post-baseline assessments. An assessment will be considered reliable if it is performed without any technical problem and if the result is within the range of plausible values.

Any repeat or additional assessments performed will be included in the individual subject data listings.

If there is a significant number of missing values for a subject (or if there is confirmed data appearing spurious), a decision will be made following consultation with the sponsor regarding the handling of these data in summaries, prior to database freeze and will be documented in the minutes of the data review.

3.2.4.2 *Missing or incomplete dates*

In all listings, missing or incomplete dates should be left as they have been recorded. However, for calculation / sorting / assignation based on dates, the following methods will be used:

The most conservative approach will be systematically considered (i.e. if the onset date of an AE is missing / incomplete, it is assumed to have occurred during the study treatment phase (e.g. a TEAE for AEs) except if the partial onset date or other data [stop date, ...] indicates differently).

A missing/incomplete date of medical history or disease diagnosis will be assumed to have occurred before any study treatment.

If a partial date and the associated information do not allow to state about the assignation to a group / category, all the possible groups / categories will be considered (e.g. a medication with partial start and stop dates could be considered as prior and concomitant treatment).

Where this is possible, the derivations based on a partial date will be presented as superior inequalities (e.g. for an AE started in 2004-02 after the administration performed on 2004-01-31, the days since last dose will be “ ≥ 2 ”, similarly the duration of ongoing AEs or medication will be “ $\geq xx$ ” according to the start and last visit dates).

3.2.4.3 *Outliers*

Any outlier which is implausible will be excluded from the analysis. For other identified outliers, the impact should be assessed by performing the statistical analysis with the actual values and at least one other analysis eliminating or reducing the outlier effect.

3.2.5 *Subject disposition*

A summary table with the description of the number of subjects in each analysis set (Screened Set, Included Set, Safety Set, ITT set and PP set) will be performed by country and overall.

A summary table with the description of the numbers of screened subjects, screening failure subjects, included subjects, treated subjects, study completed subjects (who completed the last post-treatment follow-up visit) and the number of subjects who discontinued classified by main reason of withdrawal will be performed. A figure for subject disposition and corresponding individual listings will be provided.

A summary table with the number and percentage of subjects at each visit will be performed on the safety set.

Listing with dates of assessments will also be carried out on the included population.

A listing of the inclusion and exclusion criteria not met will be provided by subject, and subject eligibility will also be listed on the included population.

A summary table will present the extent of subject duration in the study (in weeks) for all the subjects in the safety population (as defined in [Appendix 1 \(2\)](#)).

A listing of their study duration (in weeks) will be presented by subject on the safety population.

Listing of re-enrollment of subjects will be listed separately on included population.

